4.2 SCIENTIFIC RATIONALE FOR STUDY DESIGN

Accumulating data linking COVID-19 to thrombotic events has shifted equipoise away from inclusion of a placebo group. Consequently, rNAPc2 will be compared to heparin administered according to local SoC. Clinical pathways for anticoagulation of hospitalized patients with COVID-19 vary from institution to institution reflecting the current state of clinical uncertainty. To avoid potential confusion and error due to deviation from these pathways, heparin-allocated participants will receive regimens according to local institutional practice. As many hospitalized patients with COVID-19 participate in trials of antiviral and other therapies, concurrent participation in interventional trials that do not include anti-thrombotic or anti-platelet therapy is permitted. Based on data that D-dimer levels are related to patient outcomes in hospitalized COVID-19 patients,⁵ randomization will be stratified by local laboratory D-dimer level at screening.

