5 STUDY POPULATION

5.1 INCLUSION CRITERIA

Patients must meet *all* of the following inclusion criteria to be eligible for randomization in this study:

1. Age ≥ 18 years and ≤ 90 years at the Screening assessment
2. Weight ≥ 50 kg at randomization
3. Hospitalized with a diagnosis of COVID-19 and in need of inpatient medical care
4. Positive for SARS-CoV-2 on nasopharyngeal, oropharyngeal or other tissue/body fluid samples by PCR or validated other test of ongoing infection (not an antibody test for prior exposure), within seven (7) days of hospitalization or screening assessment
5. D-dimer level > upper limit of normal at screening (local lab; initial value as collected at the time of hospital admission, prior to initiation of heparin treatment preferred)
6. Provided electronic or written informed consent, either personally or through a legally authorized representative (LAR)
7. Must agree not to participate in a concurrent interventional study involving anticoagulation or anti-platelet therapy
8. Female patients of reproductive or childbearing potential must be willing to use an effective method of contraception for the duration of the study (see section 5.3.1), and male patients must be willing to use an effective method of contraception to avoid partner pregnancy and abstain from sperm donation for at least 90 days after last dose.

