6.3 MEASURES TO MINIMIZE BIAS: RANDOMIZATION AND BLINDING

Intervention Allocation

Site-based randomization will be implemented in this study. Participants will be randomly assigned to treatment groups based on a computer-generated randomization schedule prepared before the study by or under the supervision of the Sponsor. The randomization will be balanced by using randomly permuted blocks for each site and the D-dimer level stratification. After confirming eligibility, the requestor will obtain the participant's randomization assignment.

Blinding

To minimize the potential for bias, data that may potentially unblind the intervention assignment will be handled with special care to maintain the integrity of blinding for the participant and the CEC. This includes discouraging speculation and avoiding verbal disclosure to the participant and redacting the

data in question from medical records reviewed by the CEC. Study site investigators assessing potential clinical efficacy and safety events should be blinded to treatment allocation, if possible. Neither the study site, Sponsor, CEC, nor study participants will have access to the central laboratory results during the conduct of the trial with the exception of clinical safety alerts.

The investigator will not be provided with randomization codes. The study site will know the treatment assignment, however; participants should not be made aware of their treatment assignment.

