8 STUDY ASSESSMENTS AND PROCEDURES

8.1 STUDY PROCEDURES

8.1.1 SCHEDULE OF ACTIVITIES

Table 2a. Schedule of Activities (SoA)

Activity	Screen Day -7 to 1	Baseline Day 1	Day 2 (24h post-dose \pm 2h)	Day 3 \pm 1d	Day 5 \pm 1d	Day 8 \pm 1d	Day of Hospital Discharge	Day 30 \pm 3d
Informed consent	x							
Assess eligibility	x	x						
Randomize		x						
Medical history (COVID-19, cardiovascular, medical/ surgical history) ^b		x						
Concomitant medication ^b		x	x	x	x	x	x	x ^d
Baseline demographics ^b	x							
Focused physical examination, vital signs, weight, height ^b		x						
Study medication ^c		rNAPc2 7.5 μ g/kg SC on Day 1 and 5 μ g/kg SC on Days 3 and 5 or rNAPc2 5 μ g/kg SC on Day 1 and 3 μ g/kg SC on Days 3 and 5 or heparin per SoC						
Local laboratory values	x ^a	Record values of interest performed in the hospital clinical laboratory until hospital discharge or day 30 visit (whichever is first). In the case where a lab test is measured multiple times per day, the first scheduled values as well as any additional values that represent a clinically significant change should be reported.						
Assess need for inpatient medical services & complete ACTT			Daily until discharged to outpatient status or death or Day 30 reached					
Clinical & adverse events ^g	x	x	x	x	x	x	x	x ^d
Post-COVID functional status (PCFS) scale							x ^h	x ^d
Vital status								x ^d
Healthcare utilization							x	x ^d
Central Laboratory assessments (see Table 2b)		x	x	x ^e		x ^f	x ^f	x ^e

^a Local lab D-dimer drawn during hospitalization and prior to randomization will be used for eligibility and randomization stratification

^b May be obtained/extracted from medical record to minimize staff exposure to COVID-19

^c rNAPc2 must be dosed on Days 1, 3 and 5; only one rNAPc2 dose regimen is anticipated in Phase 3; Participants randomized to receive heparin will have doses administered per standard of care (SoC)

^d Participants who are discharged prior to Day 30 may have these activities performed remotely

^e For phase 2b only

^f If participant is discharged prior to Day 8, central laboratory assessments should be performed at hospital discharge

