9.4 STATISTICAL ANALYSES

9.4.1 GENERAL APPROACH

The statistical analyses described in this section will be performed as further detailed in a separate statistical analysis plan. The statistical analysis plan will supersede the protocol in the event of any differences between the two documents in the plans for data analysis, and the protocol will be amended if appropriate. The statistical analysis plan will be included as an appendix in the clinical study report for this protocol.

Descriptive statistics for continuous variables will include the number of participants, mean and standard deviation, median, first and third quartiles, and minimum and maximum values. Descriptive statistics for categorical variables will contain count and percentage.

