9.4.2 ANALYSIS OF THE PRIMARY EFFICACY ENDPOINT(S)

Phase 2b: Primary efficacy endpoint is change in D-dimer level from Baseline to Day 8, or day of discharge if prior to Day 8. The change in D-dimer will be calculated using proportional change in D-dimer level from the level at baseline to the level at either Day 8 or discharge if discharge occurs before Day 8. A Wilcoxon rank sum test will be performed to compare baseline and Day 8 (or early discharge) D-dimer levels within each treatment group. A second Wilcoxon rank sum test will be used to compare proportional change from baseline to Day 8 (or early discharge) between treatment groups. The primary analysis will involve a comparison of the pooled rNAPc2 treatment groups against the heparin treatment group. Secondary and sensitivity analyses of the primary endpoint will be conducted as described in the statistical analysis plan.

Because the optimal dose rNAPc2 is unknown and its determination is a key objective of the Phase 2b study, the assumption that both doses will be effective and thus can be pooled for statistical analysis may not be correct. Therefore, a series of secondary analyses will be conducted, consisting of analysis for dose response, effectiveness in a single dose group, effectiveness that is related to the extent of baseline D-dimer elevation, and the subgroup analyses described in [Section 9.4.7 SubGroup Analyses](#).

Missingness within the data is to be expected. Subject profile, mortality, or early discharge give rise to the possibility that nonrandom attrition may bias the point estimate for the treatment effect for the primary endpoint. Therefore, missingness will be handled by multiple imputation during a sensitivity analysis as described in the Statistical Analysis Plan (SAP).

Phase 3: The primary efficacy endpoint is time to recovery by Day 30, with day 1 being the date of randomization. Recovery is defined as the first day a participant meets criteria for category 6, 7 or 8 of the ACTT ordinal scale. The analysis of the primary efficacy endpoint will be a comparison of the two treatment groups by a stratified log-rank test, where stratification is according to local laboratory screening D-dimer level $>$ or $\leq 2X$ local laboratory ULN. Cumulative incidence by treatment group will be

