9.4.6 PLANNED INTERIM ANALYSES

Additional details of the planned interim analyses will be provided in interim analysis plans, 1 plan each for Phase 2b and Phase 3, respectively.

Phase 2b: An interim efficacy analysis will be conducted when 120 participants have completed Day 8 assessments or Day of Discharge assessments if the participant is discharged prior to Day 8. To account for early recovery, deaths, and lab errors which may lead to lack of Day 8 D-dimer in approximately 20% of patients, 120 participants will provide for approximately 100 participants to be evaluated in the interim efficacy analysis. The interim efficacy analysis will test for futility based on the primary study hypothesis. Additionally, at the interim efficacy analysis, the Data Safety Monitoring Committee will be empowered to adjust sample size as pre-specified in the Phase 2b interim analysis plan. An interim safety analysis will occur after approximately one third of the total target enrollment (i.e., 30-40 participants) completes the Day 8 assessments. Outcomes of the interim analyses may include changes to dose regimens, or other adjustments related to safety or trial logistics. No spending of type 1 error will occur during the interim analysis.

Phase 3: Interim analyses on time to recovery will occur when approximately 33% and 67% of the initial target number of events (i.e., 120 and 240) have occurred. The following is an outline of the interim analysis plan:

- Both interim analyses will include a non-binding assessment for futility; no formal boundary will be used in the first interim analysis, while the second will use a boundary corresponding to 10% conditional power.
- Both interim analyses will have a specified boundary for unequivocal efficacy corresponding to a p-value of 0.0001, 1-sided solely for the purposes of a sample size re-estimation at the second interim analysis; the study will not be stopped for unequivocal efficacy even if this boundary is crossed at one of the interim analyses.
- The interim analysis at 67% of the initial target number of recovery events will include a "promising zone" analysis of conditional power, whereby sample size may be increased by up to 150 additional participants (e.g., 600 total participants) and 120 additional events (i.e., 480 total events) to target 90% conditional power for the final analysis if conditional power, based on the estimated interim HR, is within 30% and 80%.

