7.1.1 Primary Analysis of the Primary Efficacy Endpoint

Proportional change, represented by percent change, will be calculated as $100 \times (\text{D-Dimer level at Day 8 or Day of Discharge if prior to Day 8} - \text{D-Dimer level at baseline}) / \text{D-Dimer level at baseline}$ and will be based on data provided by the central laboratory, or local laboratory paired samples if the central laboratory values are not available. The pairing process will be operationalized as outlined:

For Day 1 (baseline) paired local-local or central-central laboratory values:

1. Use any lab D-dimer drawn during the current admission and up to randomization

2. Use the laboratory sample closest to randomization if there are multiple D-dimer measurements.
3. All samples obtained more than 1-hour post-initiation of study drug are ineligible.

For Day 8 or Day of Discharge paired laboratory values:

1. Use laboratory samples collected within ± 48 h of the Day 8 or Day of Discharge study visit (whichever occurs first).
2. If there are multiple laboratory samples collected within that window, use the lab value on the target day; if not available, use the lab value immediately after the target visit day.

A Wilcoxon rank sum test will be used to compare proportional change from baseline to Day 8, or Day of Discharge if prior to Day 8, between treatment groups. The between treatment group rank sum test is considered the primary analysis of the primary endpoint.

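### The primary Wilcoxon test ignores the D-dimer stratum used in randomisation: it is valid but mildly conservative, and a stratified (van Elteren) test would be a cheap, modest improvement

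*SAP*

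**What the plan says.** **Randomisation.** Protocol 6.3: "The randomization will be balanced by using randomly permuted blocks for each site and the D-dimer level stratification". Protocol 4.1 and SAP 2.3 set the cut at twice the assay's upper limit of normal. Protocol 4.2 gives the reason: "Based on data that D-dimer levels are related to patient outcomes in hospitalized COVID-19 patients". The stratum is fixed before treatment (Protocol 8.1.1, Schedule of Activities): "Local lab D-dimer drawn during hospitalization and prior to randomization will be used for eligibility and randomization stratification".

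**Primary test.** Protocol 9.4.2: "A second Wilcoxon rank sum test will be used to compare proportional change from baseline to Day 8 (or early discharge) between treatment groups". SAP 7.1.1 keeps this for pooled rNAPc2 against heparin: "The between treatment group rank sum test is considered the primary analysis of the primary endpoint". Neither section names the stratum. SAP 5.4 brings it in only for analyses that call for it, and 7.1.1 does not.

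**Where the stratum is used.** It appears in the log-rank test and Cox model for time to recovery (SAP 7.2.2), the adjusted composite models (7.2.3) and the Bayesian subgroup model (11.2). It is also a listed subgroup (5.3).

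**What borrows the primary test.** Day 2 and Day 3 D-dimer (7.2.1), the biomarkers (7.2.4), organ support free days (7.3.2), the multiple-imputation sensitivity analysis of the primary finding (11.1) and the per-dose analyses (11.2).

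**The concern.** Stratified randomisation balances the arms on the stratum. If the stratum also predicts percent change, the true variance of the rank statistic is smaller than the one the unstratified test assumes. The test then rejects less than 5% of the time under the null and gives up some power.

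Prediction is plausible here. Patients selected for a high screening value tend to regress downwards and those with a low value upwards, so the two strata may differ in percent change without any treatment effect.

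At stake is some power for the main efficacy conclusion of Phase 2b, and consistency with time to recovery, which the SAP does stratify. Bias is not at stake.

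**Working it through.** **Inputs from the documents.** 160 randomised 1:1:2, so pooled rNAPc2 to heparin is 80:80; 20% not evaluable, so 160 × 0.8 = 128, or 64 per arm (SAP 2.2); two-sided alpha 0.05 (SAP 7.4). Stated Wilcoxon power at 128 evaluable is 71.3/83.1/88.3/91.3/94.1% for reductions of 20/25/30/35/40% (SAP 2.2).

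**Not in the documents.** The SD of log change, the baseline to Day 8 correlation (rho), the screening to baseline correlation (r), the share of patients in each stratum and the stratum effect. These are assumed below.

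**Step 1: the plan's own power row.** With Wilcoxon efficiency 3/π, the effective n per arm is 64 × 3/π = 61.1. The implied SD is |ln(1 − reduction)| / [(1.96 + z_power) × √(2/61.1)].
- 20%: 0.223 / (2.522 × 0.181) = 0.489
- 25%: 0.545
- 30%: 0.626
- 40%: 0.511 / (3.523 × 0.181) = 0.801

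The implied SD rises along the row, so no single SD reproduces it. That fits the table's footnote that the powers are averages over other simulation conditions, and is not evidence of an error. Drawing the SD afresh for each simulated trial (log-normal, median 0.415, SD of log 0.67) gives about 72/81/88/92/95%, close to the stated row.

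**Step 2: the two tests.** In stratum h, let n_h be the evaluable number, n1_h and n0_h the numbers per arm and W_h the rank sum of the rNAPc2 arm. Van Elteren uses Z = Σ[W_h − n1_h(n_h+1)/2]/(n_h+1), divided by √Σ[n1_h n0_h / (12(n_h+1))]. The plain Wilcoxon ranks all 128 together. Both were run on the same simulated trials.

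**Step 3: equal treatment effect in both strata.** Change in power (points), van Elteren minus Wilcoxon:

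| Model | Weak to moderate stratum effect | Strong stratum effect |
|---|---|---|
| Direct shift between strata, reductions 20–30% at the implied SDs | gap 0–0.5 SD: −0.4 to +1.7 | gap 0.75 SD: +1.7 to +4.3; gap 1.0 SD: +3.1 to +7.6 |
| Regression to the mean, 20 sites, blocks of 4, implied SDs, 60% above the cut | r = 0.6: +0.1 to +2.0 | r = 0.85: +0.4 to +4.2 |
| As above, SD drawn per trial, 50/50 split, reduction 20%, rho 0.3–0.7 | r = 0.3–0.7: −0.1 to +2.0 | r = 0.9: +1.4 to +3.7 |

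High r is the optimistic case. The stratum uses a local value, and Protocol 5.1 states the preferred sample: "initial value as collected at the time of hospital admission, prior to initiation of heparin treatment preferred". Screening may fall up to 7 days before baseline, and baseline is normally a central value. For local-local pairs (SAP 7.1.1) baseline may be the screening sample itself, and r then approaches 1.

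**Step 4: unequal effect.** Same model with SD drawn per trial and a 30% reduction in one stratum only.
- Low stratum only: −0.6 to −1.9 points.
- High stratum only: +0.5 to +6.3 points.

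The sign has a simple cause. With regression to the mean, low-stratum patients lie higher in the pooled ranking of percent change. A treatment shift moves them through the crowded middle, which the unstratified test rewards. High-stratum patients shift towards the lower tail, where pooled ranks change little.

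**Step 5: type I error.** In the shift model the Wilcoxon rejects 5.0%, 4.2% and 2.8% at gaps of 0, 0.5 and 1.0 SD, against 4.9–5.1% for van Elteren. In the regression-to-the-mean model with SD drawn per trial, Wilcoxon gives about 3.4–4.8% and van Elteren 4.3–5.2%. Both control the error, and the Wilcoxon is the more conservative.

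**The case against.** The case for leaving the test alone is serious. Both tests are valid. Percent change already divides by baseline D-dimer and time to recovery does not, so stratifying only the latter is not a contradiction. Protocol 4.2 links D-dimer to patient outcomes, not to percent change in D-dimer, so the documents do not show that the stratum predicts this endpoint. Without that there is nothing to gain. SAP 5.4 makes adjustment a stated choice, and the stratum is examined in subgroup work. The SAP is at version 3.0, its primary-test wording was clarified after regulatory review (Revision History), and the interim analysis may already have run.

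All of this stands, and it limits the point to an optional improvement. It does not remove the expected gain if the stratum is prognostic. The subgroup analyses do not change the primary test, and the recorded clarification concerned the signed rank test, not stratification.

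Four stronger readings are tempting and unsupported:
- *The plan is biased or its test invalid.* Type I error stays at or below about 5%.
- *The change costs nothing.* It needs no new data, but it needs a protocol departure, SAP edits, a check of the interim plan and a note to the regulator.
- *It can lose only a few tenths of a point.* That holds only for equal effects in both strata. Protocol 9.4.2 itself plans to examine whether effectiveness depends on baseline D-dimer.
- *The gain can be turned into participants saved from the SAP power table.* The documents do not fix even its sign, so such a count would be false precision.

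**Conclusion.** The point holds as a modest efficiency improvement. The planned test is valid and mildly conservative if the stratum is prognostic.

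With equal effects, van Elteren changes power by about -0.4 to +2 points for a weak-to-moderate stratum effect, and adds more if the stratum is strongly prognostic. The +2 is therefore not an upper bound. With an effect only in the low stratum it can lose about 0.6 to 1.9 points; with one only in the high stratum it can gain about 0.5 to 6.3.

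These figures rest on assumed SDs, correlations and stratum shares, and on evaluability that is random. The SAP's actual rule is a ±48-hour window followed by last observation carried forward (5.1), which was not modelled. Confidence is medium: the facts are clear and the size is not.

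**What to change.** Before unblinding:
1. In SAP 7.1.1, make the primary test a van Elteren test of percent change by D-dimer stratum as randomised, pooled rNAPc2 against heparin. Do not stratify by site: 20 sites × 2 strata leaves 128/40, about 3 evaluable patients per cell.
2. Keep the unstratified Wilcoxon as a sensitivity analysis.
3. Use the same stratified test for Day 2 and Day 3 D-dimer (7.2.1), the 7.2.4 biomarkers, the multiple-imputation analysis (11.1) and the per-dose analyses (11.2). Leave 7.2.2 and 7.2.3 as they are.
4. Reword 7.3.2 so that organ support free days names its own test and does not point to the primary analysis.
5. Record the change in SAP Section 12.
6. Check that the Phase 2b interim analysis plan uses the same test, since Protocol 9.4.6 says: "The interim efficacy analysis will test for futility based on the primary study hypothesis".
7. Tell the regulator.

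If the data are already unblinded, leave the primary test unchanged and add van Elteren as a sensitivity analysis only.

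**Cost.** No new data or participants. The change departs from the test named in Protocol 9.4.2, which Protocol 9.4.1 allows: "The statistical analysis plan will supersede the protocol in the event of any differences between the two documents in the plans for data analysis". The statistical price is a small loss of power if the stratum is not prognostic or the effect sits in the low stratum.

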7.1.2 Secondary Analysis of the Primary Efficacy Endpoint

A within treatment analysis of the proportional change in D-dimer levels will be a secondary analysis, subject to multiplicity control as for secondary endpoints. Wilcoxon signed rank tests will be used to compare within treatment group baseline vs. Day 8 D-dimer values, or Day of Discharge if prior to Day 8, values within each treatment group (i.e., rNAPc2 pooled, Heparin), (i.e., rNAPc2 pooled vs. Heparin).

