2.2 Sample Size Determination

During Phase 2b, approximately 160 participants will be enrolled and randomized 1:1:2 to rNAPc2 dose regimen 1, rNAPc2 dose regimen 2, and heparin SoC, respectively. Assuming approximately 20% of participants may not be evaluable for any reason, 160 randomized participants will provide for approximately 130 evaluable participants. At a sample size of 160, the study will have adequate power across a range of clinically meaningful effect sizes, operationalized as proportional reductions in D-dimer (relative to heparin) from 20% to 40% in increments of 5% (see below). This sample size was selected, based on a statistical simulation using Wilcoxon rank sum and assuming a 20% missing/dropout rate, to ensure inferences for the primary endpoint analysis will be robust, given certain potential confounding factors such as missing data (random or non-random), heterogeneous application of heparin (low molecular weight and unfractionated; prophylactic and therapeutic), effects of subject-level covariates (e.g., comorbidities), and effects of site-level covariates (e.g., country).

Power, Primary Endpoint							
	Effect Size (Proportional Reduction)						
	Enrolled Subjects	Evaluable Subjects	20%	25%	30%	35%	40%
Sample Size	80	64	55.8%	67.4%	75.6%	81.0%	84.5%
	100	80	60.5%	72.7%	80.1%	84.9%	87.8%
	110	88	63.6%	76.2%	80.7%	86.6%	89.2%
	120	96	65.2%	78.0%	82.8%	86.9%	91.0%
	130	104	68.2%	79.3%	84.8%	88.7%	91.7%
	140	112	68.9%	80.7%	86.6%	89.3%	92.5%
	160	128	71.3%	83.1%	88.3%	91.3%	94.1%
	180	144	74.9%	84.5%	89.5%	92.5%	94.6%
	200	160	77.2%	86.5%	91.0%	93.8%	95.8%

*Significance via $\alpha = 0.05$
 †Simulated with 20% Missing Data
 ‡Percentages as Averages Across Other Simulation Conditions

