2.4 Primary Endpoints

2.4.1 Efficacy

The primary efficacy endpoint is proportional change, represented as percent change, in D-dimer level from baseline to Day 8 or Day of Discharge if prior to Day 8.

Language pertaining to the primary efficacy endpoint in the ASPEN Protocol is operationalized as proportional change.

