7.2.4 Coagulation and Inflammation Biomarkers

The following laboratory parameters will be collected and analyzed by a central laboratory. Change from baseline to both Day 8 or discharge will be summarized for inflammatory biomarkers (IL-6, hsCRP) and coagulation biomarkers (PT, PTT, factor Xa and tissue factor). All data will be listed. Primary analyses will be by Wilcoxon-family tests as described above in the primary efficacy endpoint. For purposes of interpretation of outcomes, IL-6 and hsCRP are considered measures of systemic inflammation, PT, PTT and factor Xa are coagulation parameters, and tissue factor is the biologic target of rNAPc2. In addition,

in a subset of participants anti-phospholipid antibodies known to be generated in COVID-19 and inhibited by rNAPc2, are being measured at baseline, Day 8/discharge and on Day 30 at a specialty laboratory.

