7.4 Significance

All statistical tests and confidence intervals will use a 2-sided analysis with a significance level of $\alpha = 0.05$.

8 Safety Analysis

The following safety analyses will be based on the Safety population and on-treatment data scope. Additional safety analyses are detailed in [Section 11.4](#).

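### SAP 7.1.2 does not settle which variable the within-arm signed-rank test uses, and neither reading is reliable for right-skewed D-dimer; the log ratio should be named

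*SAP*

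**What the plan says.** SAP 2.4.1 defines the primary endpoint as "proportional change, represented as percent change, in D-dimer level from baseline to Day 8" or discharge if earlier. SAP 7.1.1 gives the formula: "Proportional change, represented by percent change, will be calculated as" 100 × (follow-up − baseline)/baseline. It makes the between-arm Wilcoxon rank-sum test the primary analysis.

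SAP 7.1.2 adds a within-arm analysis under the same multiplicity control as the secondary endpoints. It makes two statements about the variable:

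- "A within treatment analysis of the proportional change in D-dimer levels will be a secondary analysis"
- "Wilcoxon signed rank tests will be used to compare within treatment group baseline vs. Day 8 D-dimer values"

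The first points to percent change, the second to paired D-dimer levels. Protocol 9.4.2 also speaks of levels within each group (though it names the rank-sum test there) and uses proportional change for the between-group test.

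SAP 5.8 allows transformation, including the logarithm, and expects that D-dimer may need it. Its trigger is a violated normality assumption, mainly in the Bayesian models. The signed-rank test assumes no normality, so that rule does not reach it. SAP 12 keeps signed rank out of the primary endpoint analysis.

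**The concern.** The signed-rank reference distribution assumes that the analysed differences are symmetric about zero under the null. Percent change has a floor at −100% and no ceiling. A doubling scores +100 and the mirror-image halving scores −50, so when the typical ratio is 1 the rises take the larger ranks. The test can then reject because of skewness, in the direction of a rise.

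Raw differences are symmetric if baseline and Day 8 are exchangeable. If each patient's ratio is independent of baseline, the difference is baseline × (ratio − 1), which has the same right skew.

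At stake is a multiplicity-controlled secondary result. It could report a within-arm rise when the median ratio is 1, or miss a real fall. Two programmers following 7.1.2 in good faith could also run different tests and get different answers.

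**Working it through.** **Sample size per arm.** SAP 2.2 states "160 randomized participants will provide for approximately 130 evaluable participants". With 20% not evaluable, 160 × (1 − 0.20) = 128, which agrees with that figure and with the power table. Allocation is "randomized 1:1:2 to rNAPc2 dose regimen 1, rNAPc2 dose regimen 2, and heparin SoC, respectively", so pooled rNAPc2 against heparin is 1:1 and 128/2 = 64 per arm.

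**Level.** SAP 7.4: "All statistical tests and confidence intervals will use a 2-sided analysis with a significance level of" 0.05. The rates below are at that nominal level, before any multiplicity adjustment.

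**Not in the documents.** No SD for D-dimer change is given. The power table averages over simulation conditions that are not listed, so no SD can be read from it. I assume a log-normal ratio and show log SD 0.3 to 1.2.

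**The scale effect on one pair of patients.** Let baseline be B, with one patient doubling and one halving.
- Percent change: 100 × (2 − 1) = +100 and 100 × (0.5 − 1) = −50.
- Raw difference, same B: +B and −0.5B.
- Log ratio: ln 2 = +0.693 and ln 0.5 = −0.693.

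Only the log ratio treats the two as equal and opposite.

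**Simulation.** n = 64; ratio = exp(m + SD × Z), with m = 0 for no change and m = ln(0.8) for a 20% fall; two-sided signed-rank test by normal approximation; 20,000 trials per cell. The test is run on:
- 100 × (ratio − 1);
- raw differences with exchangeable log-normal pairs (correlation 0.6);
- raw differences B × (ratio − 1), with baseline log SD 0.9 and ratio independent of B;
- ln(ratio).

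The Monte Carlo standard error at a 36% rate is √(0.36 × 0.64/20,000) = 0.3 percentage points. Repeat runs agreed to about one point.

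Rejection with median ratio 1:

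| log SD | percent change | raw, exchangeable | raw, multiplicative | log ratio |
|---|---|---|---|---|
| 0.3 | 8% | 5% | 6% | 5% |
| 0.5 | 13% | 5% | 9% | 5% |
| 0.8 | 23% | 5% | 14% | 5% |
| 1.0 | 30% | 5% | 19% | 5% |
| 1.2 | 36% | 5% | 23% | 5% |

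On percent change nearly all rejections point to a rise: at log SD 0.5, 13.2 of 13.5 points; at 1.2, 36.5 of 36.6. If all 80 per arm had a value, percent change would reject about 9% at SD 0.3 and 44% at SD 1.2.

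**Detecting a true 20% fall** (an illustrative within-arm effect; the power table's reductions are relative to heparin). At log SD 0.8:
- percent change: 14%;
- raw differences: 19% if multiplicative, 49–51% if exchangeable apart from the shift;
- log ratio: 57–58%.

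Percent change against log ratio is 69% and 93% at log SD 0.5, and 2% and 29% at 1.2.

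**Primary analysis.** Percent change is an increasing function of the ratio, as is its log. The between-arm rank-sum test therefore sees the same ranks on either scale.

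**The case against.** The strongest reply is textual: the only sentence that names the test compares D-dimer values, and Protocol 9.4.2 also says levels. On that reading the test holds 5% under exchangeability and loses only some power (49–51% against 57–58% at log SD 0.8). This stands as far as it goes, and it is why the point cannot be put as a defect of percent change alone. It does not clear the plan. The opening sentence of 7.1.2 still says proportional change, and raw differences are safe only under exchangeability. SAP 2.2 frames effects as proportional reductions, which makes the multiplicative case relevant, though no document says that ratios are independent of baseline.

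Second, the log ratio's 5% follows from simulating symmetric log ratios. That is fair: the log-ratio test also needs approximate symmetry, though for a positive, right-skewed marker this is a more plausible condition than symmetry of percent change.

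Third, the consequences are limited. The trial's question is comparative, a within-arm change cannot separate treatment from natural course, and false rejections towards a rise do not flatter rNAPc2. All of this stands.

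A reader might also extend the point to SAP 7.2.4, which says "Primary analyses will be by Wilcoxon-family tests as described above in the primary efficacy endpoint". The documents do not support that. The primary test for that endpoint is the between-arm rank sum, SAP 12 excludes signed rank from it, and 7.2.4 specifies no within-arm test and speaks of change rather than percent change.

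**Conclusion.** The point holds in a limited form. SAP 7.1.2 leaves the tested variable open, and neither candidate is dependable for right-skewed D-dimer. With 64 per arm and a log-normal ratio of median 1, percent change rejects about 8% to 36% over log SD 0.3 to 1.2. Raw differences reject about 5% or about 6% to 23%, depending on how change relates to baseline.

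A reader might infer that the plan has a fixed false-positive rate of this size, or that percent change can never be near-symmetric. Neither follows. The rates rest on an assumed SD and distribution, and with small variation the distortion is slight (6.6% at log SD 0.2). Nor does the error create an apparent fall; its cost is a spurious rise or a missed fall in a secondary result. The primary between-arm test stands. The change is worth making before unblinding, but it is not critical to the trial's main conclusion.

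**What to change.** In SAP 7.1.2, state that the within-arm signed-rank test is applied to log(Day 8 or discharge value / baseline value), and reword the opening sentence to match. Report the back-transformed Hodges-Lehmann ratio with its 95% CI as the within-arm effect, and keep percent change for display. No change to 7.1.1 or 7.2.4 is needed for this point.

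The cost is one or two sentences of SAP text before unblinding, with no new data and no effect on the primary analysis. The small downside is that validity then rests on approximate symmetry of the log ratio, which can be checked by plotting it.
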